advertisement will take two weeks and it may be renewed depending on progress on recruitment. Data from these clinics indicate that several thousand patients with AD and family members have received care and supportive services from these clinics in the past year. We plan to enroll up to **50 participants** with AD and their family caregivers (1 caregiver per participant with AD) during the study to achieve a sample of **N=30** dyads as attrition rates of up to 50% are reported in the literature. Given the history of the number of persons with AD who receive care through these clinics, the applicant is confident an adequate sample size can be obtained. At each 3-month interval, recruitment goals will be assessed. Potential study participants (persons with AD and family caregivers) will be given information regarding the proposed study and will be given a consent form to take home and read. Because this is a single-group study design, there is no randomization and no control group.

A member of the study team will follow up with the potential participants to answer any questions that they may have regarding the study via telephone at a mutually agreed upon time. If the potential participants decide to enroll in the study, the study coordinator will make an appointment to visit with the potential participants at their home to gain written, informed consent. At this first visit, the study coordinator will answer any questions that the potential participants have regarding the study. In AD study participants, surrogate assent will be obtained, if needed.

The **inclusion criteria** for this study are as follows. For persons with dementia:

1) Females and males; 2) age 60-99 years; 3) physician documentation of dementia: Alzheimer's disease, vascular, mixed or unspecified type; 4) community-dwelling (living in the home); and 5) fluent in English.

For family caregivers: 1) age 21 years or older; 2) informal, unpaid caregiver who resides with the care recipient; 3) fluent in English; 4) functioning home Wifi; and 5) scoring above a 3 on the Revised Memory and Behavior Problems Checklist, a clinical cut-off point used to determine caregiver stress [24]. And the **exclusion criteria** are that persons with dementia: 1) presence of acute illness as this could lead to delirium; 2) alcohol abuse or dependence within the past 2 years (DSM-IV criteria); 3) history of significant psychiatric illness (e.g., schizophrenia).

C. Measurement/Instrumentation

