There are two important research questions this study aims to address: 1) how to generate effective and accurate recommendations; and 2) how to adapt the recommendation generation according to patients' and caregivers' feedback. To the best of our knowledge, no existing in-home health monitoring system provides this capability, instead recommendations are developed in an ad-hoc manner and generated ahead of time and independently of the interaction dynamics. Due to the nature of dementia disease and the consideration of patient safety, we will *only study recommendations for caregivers*. But the technical solutions we examined here are general, and can be applied to other health recommendation scenarios. We should note that we are not replacing medical care; study participants (e.g., caregivers) will be provided information to seek help from their regular healthcare provider or emergency services as needed.

The proposed collaborative research will take place over four years and will follow the outlined timeline:

Year One: In the first year, focus will be on building the front-end monitoring architecture. In-suites sensing and monitoring components will be built and customized for collecting the

participants' vocal and psychological signals. Joint acoustic signal analysis and text mining algorithms will be explored. At this stage of single module development, offline dataset will be used for evaluation purpose. A study consultant, will also assist the study team in developing and pilot-testing a checklist to assess for fidelity of the educational training we deliver to caregiver participants.

Year Two: We will be working on system integration and unit test of the intergraded components in the system. In the meanwhile, from the second half of year two, we will start recruiting patients for our system deployment and evaluation purpose. The PI and research assistant will work with the recruitment clinic to consent and enroll the pilot patients, collect study data, and will be on-call to answer caregiver questions as they may arise. We set “5-7 patients enrolled per month” as our recruitment milestone, and thus it takes about 2 months to recruit 8-10 patients for phase 1 pilot study and about 4 months to recruit 25 patients for phase 2 system evaluation.

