Fidelity checks will be performed , and retraining of GRAs will be performed based upon results of fidelity checks. The study team will meet weekly to ensure that recruitment and caregiver trainings are proceeding smoothly and to problem-solve with staff if necessary.

Year Three: According to our evaluation plan, we will start our second phase 4-month pilot evaluation at the beginning of year three (one month for constructing baseline measurement and three months for controlled studies). All personnel will work together to conduct the pilot study and collect feedback from real patients and clinician experts to refine the system design in an iterative way. Fidelity checks will be performed and Re-training of GRAs will be performed by based upon results of fidelity checks.

In particular, we will conduct the patient clinical interviews, and will work with an expert clinical panel to obtain feedback on the system. The caregiver interviews will be analyzed for the specifics of how the recommendation affects the caregiver-care recipient family dynamic. The monitored data, system's automated prediction results will be analyzed, and the system design and implementation revised and updated according to the patients' and clinician experts' feedback. Upon finishing the pilot study, we will start our phase 2 system-level evaluation, which will last 18 months. Note, before we start the phase 2 evaluation, we would have around 2 to 4 months period to adjust to unexpected delays/barriers in algorithm design, system development, or patient recruitment. We will make sure everything is planned and on schedule before we move onto the phase 2 system level evaluation.

Year Four: The second phase of system level evaluation will be undertaken based on the information and lessons learned from phase one. This will include new technical solutions, refined computational models and system deployment designs. All personnel will work together to conduct full system evaluation. We will collaborate with clinicians in the two study sites at Ohio State University Medical Center the in our user study Clinicians, will help us recruit patients for participation and provide feedback on the system development.

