Importance of the Knowledge to Be Gained. There may be immediate benefit to the subjects participating in the study, although we do not guarantee this, as family caregivers will be given specific knowledge and helpful reminders to mitigate potentially problematic behaviors regarding care of their loved one with ADRD. If successful, the knowledge gained will be important because of its substantial potential to enhance the treatment of difficult to manage, prevalent, and burdensome care problems of persons with ADRD, increasing their quality of life, reducing caregiver burden, delaying or reducing institutionalization, and decreasing the costs of caring for persons with AD in the future.

E. Internal Validity

The purpose of this study is primarily to establish feasibility and test the model. If we can establish that our system reduces emotional reactivity and that patient and caregiver self-reported and observed outcomes improve over time compared to an individualized baseline period, we will have established justification for a more comprehensive design that will more fully test this system against a credible alternative.

Thus, the caregivers will fill out the measures provided to them and then their interactions with the patients will be monitored for a month to establish a baseline of functioning. We will assess levels of reactivity during caregiver-patient interactions and the time it takes for them to return to their own baseline. At the end of the one-month assessment period, the caregiver will be brought in for training on the recommendations, after which they will receive recommendations when the system detects emotional reactions when the caregiver and patient are with each other. The recommendations will be personalized over time. Effectiveness of the recommendations will be assessed by examining whether the recommendations reduce the frequency and intensity of the negative patient-caregiver interactions and the time required for reactivity to return to baseline in real time, as assessed by information recorded by the monitoring system. Effectiveness also will be assessed by monitoring change in the self-report measures during the baseline period compared to the period in which the caregiver is receiving the recommendations.

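### The enrolment cap of 50 dyads does not cover the 50% attrition cited for it: 25 dyads would remain, against a target of 30

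*Protocol*

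**What the plan says.** The sample size is set out in one sentence of the protocol, section B (Sample). Enrolment is capped at 50 participants with AD and their family caregivers, and the wording "1 caregiver per participant with AD) during the study to achieve a sample of" N=30 makes both numbers counts of dyads. The reason follows directly: "dyads as attrition rates of up to 50% are reported in the literature".

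The same section adds that "At each 3-month interval, recruitment goals will be assessed", and it expresses confidence in reaching an adequate sample because of the number of patients the clinics see. Section D (Detailed study procedures), Year Three, allows slack before phase 2: "we would have around 2 to 4 months period to adjust to unexpected delays/barriers in algorithm design, system development, or patient recruitment". Section E (Internal Validity) gives the aim: "The purpose of this study is primarily to establish feasibility and test the model". No other attrition figure, no planning rate and no power or precision calculation appears in the protocol.

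**The concern.** The sentence offers the attrition figure as the reason for enrolling more than 30 dyads. A natural reading is that the step from 30 to 50 was sized to absorb attrition as high as the rate named. The arithmetic does not bear that out. What is at stake is the accuracy of the protocol's only sample-size justification. A reader may believe that the plan tolerates losing half the dyads and still ends with 30, when its tolerance stops at 40%. In a feasibility study retention is itself of interest, so the attrition that the target can bear should be stated correctly.

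**Working it through.** **Inputs** (all from section B, Sample)
- Maximum enrolment: 50 dyads.
- Target after attrition: 30 dyads.
- Cited attrition: up to 50%.
- Single group, so no allocation ratio enters.

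**Step 1. Try to reproduce the plan's 50 from 30 and 50%.**
- Usual inflation, N/(1 − d): 30/(1 − 0.50) = 60.
- The common incorrect shortcut, N × (1 + d): 30 × 1.50 = 45.
- Neither gives 50, and the gaps (10 and 5 dyads) are too large for rounding.

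**Step 2. Work forward from the cap.** Expected dyads remaining = 50 × (1 − d), and enrolment needed for an expected 30 = 30/(1 − d), rounded up:

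| Attrition d | Remaining from 50 | Enrolment needed for 30 |
|---|---|---|
| 30% | 35 | 43 |
| 40% | 30 | 50 |
| 45% | 27.5 | 55 |
| 50% | 25 | 60 |

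**Step 3. Find the break-even.** 1 − 30/50 = 0.40. The cap of 50 matches the target at 40% attrition, not at 50%. At 50% the shortfall is 30 − 25 = 5 dyads.

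**Step 4. Allow for chance.** The figures above are expectations. If dyads drop out independently (an assumption; the protocol says nothing on this), the number remaining from 50 is binomial. The probability that at least 30 remain is 0.561 at 40% attrition and 0.101 at 50%. These values only illustrate the gap, because the protocol attaches no pass or fail criterion to reaching 30.

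**Step 5. Look for anything elsewhere that closes the gap.** The three-monthly review assesses recruitment goals, and the 2 to 4 month allowance in section D absorbs delays. Neither raises the cap of 50 or provides for replacing dyads that leave. Clinic volume bears on how easily dyads can be recruited, not on how many are retained from a capped number.

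**The case against.** The strongest reply is that the 50% describes the top of a range reported elsewhere. The protocol does not call it the expected rate, and it does not say that 50 dyads yield 30 when half are lost. If the team privately expected 40% or less, the cap of 50 is adequate. This stands as far as it goes: it rules out saying that the study will miss N=30. It does not rescue the justification, because no lower rate is stated and the upper bound is the figure placed beside the margin to explain it.

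A second reply is that little depends on 30 rather than 25. That also stands. A reader might infer that the study would be underpowered, but the protocol makes no power or precision claim that could fail.

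A reader might also turn to section D, Year Two, which puts phase 1 at 8 to 10 patients and then allows "about 4 months to recruit 25 patients for phase 2 system evaluation". These counts add up to 33 to 35, and the reader might infer either a contradiction with section B or a count of completing dyads. The text supports neither. The total lies within the cap of 50. The counts are derived in the same sentence from a monthly enrolment milestone of 5 to 7 patients (25 over 4 months is 6.25 a month), so they are enrolment counts. Whether phase 1 dyads count towards N=30 is a matter that may be left to the SAP, which is not at hand. No finding is made on these points. The counts do show that enrolling 50 should not be taken for granted, so any corrected sentence has to be conditional on it.

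**Conclusion.** The point holds in a narrow form: the enrolment margin does not cover the upper bound cited to justify it. With the full 50 dyads enrolled, an expected 25 remain at 50% attrition, 30 would require 60 enrolled, and the target is met in expectation only at attrition of 40% or less. This rests on three numbers in one sentence and on reading N=30 as the sample left after attrition, which is how that sentence uses it. Independence of dropouts is needed only for the two probabilities.

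It is a minor error of justification. It does not show that N=30 is unattainable, and it disturbs no stated analysis or conclusion.

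**What to change.** Restate the sentence in section B so that it says two things: if the full 50 dyads are enrolled, N=30 is expected only with attrition of at most 40%; and at the cited upper bound of 50%, about 25 dyads would remain.

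The cost is one sentence and a slightly less favourable account of the margin. The target of 30, the cap of 50, the phase counts and the timeline all stay as they are.

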The specific **instruments** we will use in our evaluation include:

1) *San Diego Capacity to Consent form*: In order to determine the capacity for consent, we will use the University Of California San Diego Brief Assessment Of Capacity to Consent (UBACC). This form takes less than 5 minutes to complete and psychometric testing showed that scores greater than 14.5 were 89% sensitive and 100% specific for determining capacity to consent for research [40]

2) *Demographic form/Medical History form*. Demographic form will be used to record participant demographics (e.g., age, gender, ethnicity, time of dementia diagnosis, and months of caregiving experience, caregiving hours per day). Medical history form includes current

medications and co-morbidities. Both are for purpose of describing the study sample. This instrument will be administered at baseline and is completed by the caregiver.

3) *Cognitive status.* The Telephone Interview of Cognitive Status (TICS) will be administered over the phone to determine cognitive status. The instrument has been shown to be clinically relevant and comparable to the Mini-Mental State Examination [30]. Higher scores on the TICS indicate higher cognitive functioning. This instrument will be administered to the subject with ADRD at the screening visit after consent is obtained. AD8 will be administered to ONLY those participants recruited from a community-based setting. This brief measure screens for changes in cognitive function related to dementia as opposed to changes due to normal aging. This scale shows desirable sensitivity (.74-.85) and specificity (.84-.86) [43]. There are eight questions on this scale, and answers to the questions are dichotomous: yes or no. Scoring is measured by calculating the number of items answered as “yes, a change [44].” The Range of scores is from 0 to 8. A score of 2 or greater indicates the individual’s cognitive decline is likely dementia related [44]. The AD8 scale will be used in place of physician documentation of ADRD in the community-based setting.

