4) *Caregiver assessment of disruptive behaviors and the impact of these behaviors on caregivers.* The Revised Memory and Behavior Problems Checklist (RMBPC) is a 24-item, caregiver-report measure of observable behavioral problems in dementia patients and the caregiver’s stress reactions to these behavioral disturbances. The instrument provides a total score and 3 subscale scores for patient behavioral problems (memory-related, depression, and disruptive behaviors) and corresponding scores for caregiver reactions to each of these. Overall scale internal consistency of the instrument is reported as .84 for patient behavior and .90 for caregiver reaction and the instrument has confirmed validity through comparison of instrument scores with measures of depression, cognitive impairment, and caregiver burden [31].

5) *Depressive symptoms, anxiety, and stress:* The DASS is a set of three self-report scales designed to measure the negative emotional states of depression, anxiety and stress. The DASS was constructed not merely as another set of scales to measure conventionally defined emotional states, but to further the process of defining, understanding, and measuring the ubiquitous and clinically significant emotional states usually described as depression, anxiety and stress. As the scales of the DASS have been shown to have high internal consistency and to yield meaningful discriminations in a variety of settings, the scales should meet the needs of both researchers and clinicians who wish to measure current state or change in state over time (e.g., in the course of treatment) on the three dimensions of depression, anxiety and stress [36-38].

6) *Caregiver Strain: Modified Caregiver Strain Index* It is a 13-item self-report measure that examines both subjective and objective elements of caregiver strain. The MCSI showed excellent inter-item and test-retest reliability and was correlated in expected directions with relevant criteria [32]. It has excellent reliability and validity, displays adequate clinical sensitivity, has an established cut-off for determining functional/dysfunctional systems, and has been used successfully on a variety of mental health outcomes [28]. We will use a practice tracking worksheet to assess how much the caregivers practice the exercises over the course of the study.

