Our general plan is that by the end of this project, we will have a deployed practical system for the proposed in-home dementia patient care, and it will be ready for future clinical trial on larger and more diverse populations. All PIs will work very closely with the students on all the research

topics, aiming at regular publications in major conferences/journals. We will provide programming interfaces to the algorithms developed in this project, e.g., activity recognition and joint acoustic signal and text analysis, transfer learning and multi-task learning algorithms, and interactive feedback modeling and recommendation generation, through the developed system.

Study Visits:

Screening: Potential participants will be recruited from the geriatrics/internal medical clinic and the Center for Cognitive and Memory Disorders clinic at The Ohio State University as well as from community-based settings across Ohio state. The community sample will be obtained through Facebook posts by CCTS. The uploaded post on Facebook will be shared with other organizations and State agencies providing caregiving or ADRD resources. Communications made to the community will use the same language as the brochure provided to individuals in the Memory Clinic setting. Following screening for inclusion and exclusion criteria, potential participants will be contacted regarding their interest in the study. A study brochure will be given to the potential participants and, if they are interested in participating, a follow-up telephone call appointment will be made to review the study and to answer any questions the participants may have. If they are interested in participating, an appointment for a home visit or telephone/Zoom call will be scheduled at a mutually-agreed upon time. Prior to visit one participants will provide verbal consent/assent via telephone/Zoom. If participants provide verbal consent they will be asked to sign either an in-person or electronic consent (via REDCap) form at the time of visit one.

Participants will be in the study for up to four months from the time of consent to the time of final study data collection and interview. However, the overall study duration may be longer than the planned duration (4 months), depending on the interview schedule for you. There will be either 4 study visits at your home or 4 telephone or video calls and each will take approximately 30 – 135 minutes.

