Visit 1: The study information brochure and the study consent forms will be reviewed in person, via video call, or via telephone with the potential study participants. Written, informed consent will be obtained for both the family caregiver and the persons with dementia. If informed consent is unable to be obtained for the person with dementia based upon their scores on the Capacity to Consent instrument, their surrogate decision-maker will provide informed consent and assent for the person with dementia will be ascertained by the study team member. If willing, participants will be asked to sign for consent electronically using a REDCap link sent via email. In REDCap participants will provide electronic signatures on the consent form indicating they agree to participate in this study. Following the consenting procedure, the acoustic monitor (microphone) and accompanying laptop computer (for transferring the acoustic data to the Cloud for translation processes to occur) will be placed in the participant's home at the location that is amenable to the study participants. We anticipate this will be the kitchen/dining area and the living room areas of the home as many interactions occur in these locations. No acoustic monitoring will occur in any areas of the house that they do not wish to have a microphone placed. A 5-minute audio

recording will be obtained from the caregiver and person with dementia. The recording will be uploaded to the recommender system to generate a person ID for vocal recognition during the study.

The acoustic monitoring will occur for up to 1 month to establish baseline interactions between the family caregiver and the persons with dementia. A Smart Phone will be given to the caregiver for use during the study period for the purpose of receiving recommendations and providing feedback through daily and weekly online surveys. Written and verbal instructions on the use of the acoustic monitoring and the Smart Phone will be provided to study participants. There are no steps that participants need to follow to maintain the equipment, other than keeping the microphone and laptop plugged in to an electric outlet and recharging the Smart Phone. We will also ensure the internet connection via Wifi is enabled.

The following surveys will be administered via paper and pencil forms or RedCap to the family caregiver:

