1. DASS
2. DERS-16
3. Five Facet Mindfulness Questionnaire
4. Revised Memory and Behaviors Problem Checklist
5. Modified Caregiver Strain Index
6. Family Assessment Device
7. An emergency plan will be formulated with the family caregiver to further reinforce that our study is not a substitute for their seeking medical care for themselves or for their loved one with dementia.

For dementia study participants, we will administer these surveys:

1. AD8 (for participants from community-based settings only)

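### RMBPC and AD8 eligibility can be scored only after consent and enrolment, and the single pre-intervention RMBPC appears to serve as both entry score and baseline

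*Protocol*

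**What the plan says.** - **Order of screening.** Protocol III.D, Study Visits, Screening: "Following screening for inclusion and exclusion criteria, potential participants will be contacted regarding their interest in the study".
- **Caregiver criterion 5.** III.B Sample requires "scoring above a 3 on the Revised Memory and Behavior Problems Checklist, a clinical cut-off point used to determine caregiver stress". III.C item 4 describes the instrument as a "24-item, caregiver-report measure of observable behavioral problems in dementia patients and the caregiver’s stress reactions to these behavioral disturbances", with a total score, three subscale scores and matching reaction scores. The criterion does not say which score is meant.
- **Community recruits.** III.C item 3: "The AD8 scale will be used in place of physician documentation of ADRD in the community-based setting". A score of 2 or more is the threshold given there.
- **Visit 1.** Written consent comes first. Then "Following the consenting procedure, the acoustic monitor (microphone) and accompanying laptop computer" are to be placed in the home. The survey lists follow. The caregiver list contains "4. Revised Memory and Behaviors Problem Checklist" and the list for participants with dementia contains "1. AD8 (for participants from community-based settings only". Neither instrument is scheduled at any other point before the training at Visit 2.
- **Enrolment.** The risk-minimisation text in III.D makes signing the consent form the point of enrolment. Under the COVID-19 procedures, the consent form is delivered together with the equipment.
- **Use of the scores.** III.A describes one group with no control. III.E judges effectiveness partly by change in the self-report measures between the baseline period and the recommendation period.

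**The concern.** A caregiver-reported score cannot be known before the caregiver is contacted, so the stated order cannot be followed for criterion 5. The same holds for the AD8 in people recruited through social media, for whom no clinic record is relied on. Two things are at stake.

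1. A dyad can take up one of the 50 enrolment places, and in the contact-free route receive equipment, before anyone knows whether it qualifies. The protocol does not say what happens to a dyad that fails.
2. If those who fail are removed, caregivers are selected for high RMBPC scores, and the same scores appear to be the starting point for measuring change. High scores fall on average at the next measurement through regression to the mean. With no control group, that fall cannot be separated from an intervention effect.

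**Working it through.** **Sequence check.** Each criterion was traced to the point where it is collected.

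- RMBPC: needed for caregiver eligibility (III.B), reported by the caregiver (III.C), scheduled at Visit 1 after consent (III.D).
- AD8: needed for community eligibility (III.C), scheduled at Visit 1 after consent (III.D).
- Enrolment: at signature (III.D), hence before either score exists.
- TICS: III.C places it at a screening visit held after consent, which also disagrees with the Screening paragraph.

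**Enrolment places.** III.B plans up to 50 dyads to obtain 30. The figure 50 reproduces at 40% attrition (30/0.60 = 50). At the quoted maximum of 50%, 50 dyads leave 25; that is a separate matter. If a share s of the 50 fails at Visit 1 and still counts, 50(1 - s) eligible dyads remain, and the retention needed for 30 completers is 30/[50(1 - s)]. The values of s are assumptions:

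- s = 0: 30/50 = 60%
- s = 10%: 30/45 = 67%
- s = 20%: 30/40 = 75%
- s = 30%: 30/35 = 86%

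**Regression to the mean, if failing caregivers are removed.** The protocol supplies no score distribution, share excluded or retest correlation. Assume a normal score with equal variance at both times, share q excluded by the cut-off, and retest correlation r. Let c be the standard normal quantile of q. Selected caregivers average λ = φ(c)/(1 - Φ(c)) SD above the mean of all those screened, and the expected fall at the next measurement with no effect is (1 - r)λ.

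| q | c | λ | r = 0.9 | r = 0.8 | r = 0.7 |
|---|---|---|---|---|---|
| 10% | -1.28 | 0.195 | 0.02 | 0.04 | 0.06 |
| 25% | -0.67 | 0.424 | 0.04 | 0.08 | 0.13 |
| 50% | 0 | 0.798 | 0.08 | 0.16 | 0.24 |
| 75% | 0.67 | 1.271 | 0.13 | 0.25 | 0.38 |

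For example, at q = 50% and r = 0.8: 0.2 × 0.798 = 0.16 SD.

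**What that could do to a test.** The protocol names no test, so a two-sided 5% paired comparison with 30 dyads is only an illustration. The SD of change after selection is √[(1 - r)²V + 1 - r²], with V = 1 - λ(λ - c). At q = 25% and r = 0.8 the unrounded fall is 0.085 and this SD is 0.618. The standardised shift is 0.085/(0.618/√30) = 0.75, and the chance of rejecting with no effect is about 12% by normal approximation. Over r = 0.9 to 0.7 that chance is about 6-7% at q = 10%, 8-15% at q = 25% and 17-43% at q = 50%.

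**If failing caregivers are kept.** Criterion 5 excludes nobody, and this source of regression to the mean is absent.

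**The case against.** The strongest reply is that the Screening paragraph describes a chart pre-screen for age and diagnosis, with instrument-based screening after consent. Consent before research instruments is ordinary practice, III.C refers to a screening visit after consent, and the COVID-19 screening form allows for a subject not yet enrolled. This shows that a screening status exists. It does not supply a rule for failures, and it does not square with enrolment at signature. A chart also cannot provide the RMBPC for anyone, or the AD8 for community recruits.

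Three stronger readings are tempting, and the text does not support them.

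- *Ineligible dyads are enrolled and stay in the study.* The protocol shows only that dyads can be enrolled before eligibility is known. How many would fail, and what would be done with them, is not stated.
- *Equipment is always installed before the scores are taken.* In the Visit 1 text this is only the order of description. III.E has caregivers complete the measures before monitoring starts. The contact-free route establishes delivery before scoring, not monitoring before scoring.
- *Both harms occur together.* They need opposite handling of failures. The bias requires removal, and loss of the criterion requires retention.

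It is also fair to say that the RMBPC is not named as a primary outcome. Its end-of-study administration is implied by the Visit 4 measures and III.E rather than listed, and the study is described as mainly about feasibility. The sensor-based outcomes (frequency, intensity and recovery time) do not use the RMBPC score. These points limit the reach of the problem without removing it.

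**Conclusion.** The point holds in limited form. The stated order cannot be followed for the RMBPC or the community AD8, enrolment comes before eligibility is known, and failures have no stated consequence. If failing caregivers are removed, an RMBPC improvement of roughly 0.02 to 0.38 SD is expected with no intervention effect. The low end applies if the cut-off excludes few caregivers, the high end if it excludes most. That range rests on assumed normality, retest correlation of 0.9 to 0.7 and exclusion of 10% to 75%. It is a range and not an estimate, because the protocol fixes none of these inputs and does not say which RMBPC score the cut-off of 3 refers to. The double use concerns the RMBPC only, not the AD8. Severity is low: a worthwhile improvement, not a threat to the study's feasibility aim.

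**What to change.** 1. State one order in III.B, III.C and III.D: written consent, then eligibility scoring on the RMBPC and (for community recruits) the AD8, then activation of the equipment. Scoring need not move ahead of written consent.
2. Say what happens to a dyad that fails, and count a dyad toward the 50 only after eligibility is confirmed.
3. Take a second RMBPC, separate from the eligibility score, and make it the only baseline for RMBPC change. Visit 2 suits this, at the end of the baseline period and before training. It largely removes the regression effect, because selection no longer acts on the value from which change is measured.
4. Name the RMBPC score to which the cut-off applies.
5. Reconcile who answers the AD8. The Visit 1 list places it with participants with dementia, while the title of the reference cited for it describes an informant interview.

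The cost is one repeat of a 24-item checklist per caregiver at a visit already planned, a small addition to the survey burden that the protocol lists among its risks. The other changes are wording only.
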